## Attribution of Events

Code	Descriptor	Relationship (to primary investigational product and/or other concurrent mandated study therapy or study procedure)
UNRELATED CATEGORY		
1	Not Related	The adverse event is clearly not related: there is insufficient evidence to suggest a causal relationship.
RELATED CATEGORIES		
2	Possibly Related	The adverse event has a reasonable possibility to be related; there is evidence to suggest a causal relationship.
3	Related	The adverse event is clearly related.

Any SAE considered possibly, probably, or definitely related will result in halting of the study while an analysis of the event is undertaken. Any halting of the study and the circumstances involved will be reported to the NIH Medical Monitor within 24 hours. An Independent Safety Monitor (ISM), who is an Infectious Disease physician not

associated with the study, will review any SAE considered possibly, probably, or definitely related, prior to discussion with the research team. When sufficient information is available, the PI, the ISM, and the NIH Medical Monitor, will determine if and when the study can proceed with additional subjects and under what conditions.

Death or serious injury caused by the Nanopass device and device malfunctions will be reported to the manufacturer as per memo of understanding between the manufacturer and the FDA.

Any subjects who experiences an SAE considered related after the first dose of Shingrix vaccine will not be given a second dose.

#### **F. Potential Scientific Problems**

1. Recruitment will take considerable effort. Potential challenges include the invasive procedures (punch biopsy) involved, and finding persons in the community who've never received HZ vaccination.
2. DNAemia may not be absolutely equivalent to viremia.
3. Early events in skin may not mimic those in ganglionic environment.
4. vOka challenge may not be similar to natural infection with VZV. Immune response to each may be different.

#### **G. Data Analysis Plan**

An independent bio-statistician will review data prior to submission for publication.

##### For analysis of kinetics of DNAemia:

For sample size estimation, we assumed an incidence of viremia of 86% in the ZVL group and a  $\geq 2$ -fold reduction in the RZV group. The 2-fold reduction is a conservative estimate, considering that the efficacy is 2.9-fold higher 5y after RZV vs. ZVL. With 19 participants per group, we have 80% power to detect a 2-fold difference in viremia with  $\alpha=0.05$ . However, a larger sample size is needed to achieve the 2ary objectives. 35 participants per group will allow us to have sufficient power in correlation analyses of our primary outcome measure with 2 measures of the immune responses, which may represent clusters of several analytes that group together using PCA or other dimensionality reduction method. For the primary objective, logistic regression models will be fit using VZV DNAemia defined in Section 13.2. as a dependent variable and vaccine group as the primary independent variable and adjusted for potential confounders such as age at vaccination, age at ID vOka challenge, sex, and/or race as appropriate. For all regression models fit to the data, 95% confidence intervals will be reported based on Wald statistics in conjunction with appropriate asymptotic normal distributional theory. Secondary analyses will include the duration of DNAemia defined as the last day after ID vOka administration when the VZV DNA PCR

Relative change in percentages between groups	Total sample size (50% of total in ZVL group and 50% in SRX group)
50%	70
65%	60
80%	45
90%	25

was positive, the magnitude of VZV DNAemia, defined as the peak viral load, and the occurrence of VZV RNAemia defined as  $\geq 1$  VZV RT-RNA PCR positive result during the first week after the ID vOKA challenge.

For analysis of soluble factors and phenotypic markers:

We will generate descriptive tables of response and compare soluble factors and phenotypic markers between the 2 groups using multivariate analysis methods. We will use Hotelling's T2 test for the flow cytometric and soluble factors. We will adjust the outcome measures for potential confounders and redo the T2 test. If necessary, outcome measures will be log-transformed in order to better satisfy the assumptions of the T2 method. Cross sectional pairwise comparisons of gene expression will be made at 0, 1, 3 and 7d between groups using the DESeq2 package. Genes differentially expressed at day 0 will be filtered out at subsequent time points to avoid confounders unrelated to the intervention. Differentially expressed genes of interest at 1, 3 or 7d will be validated by RT-qPCR and used as input for downstream gene ontology pathway analysis. We will use the lists from each time point to investigate trends in gene expression over time (e.g. Is gene A upregulated at all time points?). Due to the large number of tests, False discovery rate (FDR) will be controlled at the level of 0.05.

For analysis of soluble markers and relationship to transcriptomic results:

We will generate descriptive tables of vOka replication and immune responses from all parameters by vaccine groups. We will use generalized linear models (GLM) to identify correlates between local vOka replication and viremia and between local and systemic APC, NK and Tconv, soluble markers and gene expression. Correlations will be examined between biopsies and systemic data collected at the same, preceding, and following time points. We will adjust for age and gender as appropriate and use FDR p-values.

For analysis of systemic and local immune responses that limit viremia:

With the different biological measurements, the major analytical goal will be to determine biomarkers that serve as intermediates in the pathway between virus challenge with DNAemia. With all the matched measurements (transcriptomic, soluble marker, VZV-CMI T cell responses) on the same subjects, we will use mediation analysis methods (15) in order to evaluate the mediation potential of these markers. As a primary analysis, we will create a composite mediation score based on the following linear combination:  $V_i = \sum_{m=1}^M \beta_m X_{mi}$ , where  $\beta_m$  denotes an association between molecule m with the exposure, and  $X_{mi}$  is the measurement on molecule m for subject i,  $i=1,\dots,n$ . Upon standardizing V, we then can test for mediation using the approach in Vittinghoff et al. (16). Based on the available  $n = 70$ , we performed power analyses based on the Vittinghoff et al. approach to evaluate power for mediation of the composite marker. We assumed that the probability of outcome is 56% based on our preliminary data and that we are testing at a significance level of 0.05. Using the powerMediation package in R (<https://cran.r-project.org/web/packages/powerMediation/index.html>), with the given sample size, we will have at least 80% power of identifying mediating effects of V that

are at least 1.96 on the log odds ratio scale based on the proposed extended Sobel test given in Vittinghoff et al. (16).

Sample size: Sample size is 70. Calculation for predictability of this sample size is described above.

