### Specific Aims/Study Objectives

**Primary Objective 1.** To compare the rate of vOka DNAemia within 7 days after ID vOka administration in adults who received RZV or ZVL >5y before the challenge.

**Primary Objective 2.** To compare the rate of vOka DNAemia after ID vOka challenge at <1y after RZV or ZVL vaccination and at >5y after vaccination.

**Secondary Objective 3.** To identify the characteristics of the immune responses to RZV that predict the immunologic control of vOka DNAemia after ID vOka challenge at <1y and at >5y after vaccination.

*Note:* This will include studies to further define epitope-specific immune responses, and will measure transcript profile and epigenetic changes in immune cells following vaccination.

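### The adjusted DNAemia odds ratio is fitted by ordinary logistic regression with Wald intervals and no sparse-data rule; at the plan's own rates it is overstated by about 19–33%.

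*Combined protocol and SAP*

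**What the plan says.** Section IV.G, under the analysis of kinetics of DNAemia, makes a logistic model the primary analysis. Vaccine group is the main predictor, and the model is "adjusted for potential confounders such as age at vaccination, age at ID vOka challenge, sex, and/or race as appropriate". For every regression, "95% confidence intervals will be reported based on Wald statistics in conjunction with appropriate asymptotic normal distributional theory". Section IV.G names no penalised, exact or profile-likelihood alternative, and no rule for an empty cell or a model that does not converge.

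The planning figures are in the same place: "we assumed an incidence of viremia of 86% in the ZVL group", with at least a 2-fold reduction under RZV, and "The 2-fold reduction is a conservative estimate". The plan states "With 19 participants per group, we have 80% power to detect a 2-fold difference in viremia" and then enrols 35 per group for the secondary objectives. A small table beside this text lists relative changes of 50% to 90%.

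Primary Objective 2 (section I) is "To compare the rate of vOka DNAemia after ID vOka challenge at <1y after RZV or ZVL vaccination and at >5y after vaccination". Hypothesis 2 expects the RZV rate to be the same at both times. No model is set out for this comparison, but the Wald sentence would govern any regression used for it.

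**The concern.** With 35 per group and a ZVL rate of 86%, the ZVL arm has very few DNAemia-negative participants, and the model may carry five slopes. Maximum-likelihood log odds ratios are biased away from zero in this setting, and the bias grows with each covariate. The affected quantity is the estimate for Primary Objective 1, at the plan's base-case rates.

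A second, conditional issue is that if RZV suppresses DNAemia almost completely, a cohort could have no events at all. A Wald interval for the odds ratio then does not exist. With no stated fallback, the remedy would be chosen after the data are seen.

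**Working it through.** **Inputs from the documents.** ZVL rate 86%; RZV rate 86%/2 = 43%; 35 per group; up to four covariates plus vaccine group; largest reduction in the table 90%; overall outcome probability 56% (mediation power paragraph of section IV.G).

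**The plan's own figure.** Two-sided α 0.05, 80% power, pooled variance under the null, mean rate 0.645:

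n = [1.96·√(2·0.645·0.355) + 0.842·√(0.86·0.14 + 0.43·0.57)]² / 0.43² = (1.326 + 0.509)² / 0.1849 ≈ 18.2, rounded up to 19. The stated 19 per group is reproduced.

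**True odds ratio.** (0.86/0.14)/(0.43/0.57) = 6.143/0.754 = 8.14; log 2.097.

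**Sparseness.** Expected negatives: ZVL 35 × 0.14 = 4.9; RZV 35 × 0.57 = 19.95; total about 25. With five slopes that is about 5 negatives per slope.

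**Bias at 86% vs 43%.** The unadjusted row for maximum likelihood is exact binomial enumeration over tables with no empty cell. The other figures are from simulations of 4,000 trials each, 35 per group, with no covariate effect on outcome; ranges cover separate simulations. Odds ratios are geometric means.

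| Model | Maximum likelihood OR | Excess over 8.14 | Firth OR |
|---|---|---|---|
| Unadjusted | 9.0 | about 10% | 8.1–8.2 |
| Age, sex | 9.7–9.9 | 19–21% | 8.2–8.3 |
| Both ages, sex, race | 10.7–10.8 | 32–33% | 8.3–8.4 |

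The median maximum-likelihood odds ratio is less inflated: 8.73 unadjusted, 9.1–9.2 with age and sex, about 10.1–10.2 with all four. Wald coverage is 95–96% throughout, and coverage with Firth is about 96%. The vaccine term was not estimable in about 0.7% of the adjusted runs.

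**When the Wald interval is undefined.** For a cohort with rate p, P(0 events in 35) = (1 − p)³⁵. For two RZV cohorts at the same rate, P(at least one empty) = 1 − [1 − (1 − p)³⁵]².

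- p = 43%: 0.57³⁵ ≈ 3 × 10⁻⁹, so about 6 × 10⁻⁹ for two cohorts.
- p = 26%, the RZV rate implied by 56% overall with equal groups (2 × 56 − 86): about 0.005%.
- p = 8.6%, from applying the 90% row to 86%: 0.914³⁵ = 4.3%, so 8.4% for two cohorts. In the remaining tables Wald coverage is 99.6%, so the intervals are too wide. Profile penalised-likelihood coverage is about 95.7%.

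For ZVL 86% vs RZV 8.6%: P(no ZVL negatives) = 0.86³⁵ = 0.5%, so P(an empty cell) = 1 − (1 − 0.0051)(1 − 0.0430) = 4.8%.

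**The case against.** The strongest reply is that the quoted sentence concerns intervals, and an interval method cannot move a point estimate. That is right. A reader might infer that the Wald rule inflates the odds ratio; it does not. The inflation is small-sample bias of maximum likelihood, and changing only the interval would leave it in place.

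The bias is also modest relative to sampling error. With age and sex it is roughly 0.18–0.19 on the log scale (ln 1.194 to ln 1.214), against an unadjusted standard error of √(1/30.1 + 1/4.9 + 1/15.05 + 1/19.95) ≈ 0.59. The direction of the conclusion would not change. About 0.10 of the bias is present with no covariates.

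Two stronger readings are tempting, and the documents do not support them:

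- *The within-RZV comparison often has no interval.* At 43%, or at the implied 26%, the risk is practically nil. The 8.6% rate is not stated anywhere: it applies the last row of a table with no stated baseline to 86%. That table gives 70 in total for a 50% change where the text gives 2 × 19 = 38, so its basis is unclear.
- *Wald tests lose power as the effect grows.* At 86% vs 8.6%, rejection is 95.2% if empty-cell tables count as non-rejections. The whole shortfall is the 4.8% of tables with an empty cell; Wald rejects in virtually all the others. The plan also ties Wald statistics to intervals and does not name the test.

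Race can be sparse enough for its own coefficient to separate, but the documents make race optional, and its separation does not by itself remove the vaccine interval.

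**Conclusion.** The point holds as a moderate, inexpensive improvement. At the plan's own rates and sample size, the stated model gives an adjusted odds ratio about 19–33% too high on the geometric mean, while its Wald interval covers at about the nominal level. Interval failure is a tail risk that depends on RZV DNAemia being rare, and the plan has no rule for it.

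Assumptions that are not in the documents: no true covariate effects, so that 8.14 is also the adjusted odds ratio; balanced sex; about 10% in the minority race category; age at vaccination almost collinear with age at challenge; no dropout. The inflation figures are conditional on a finite estimate. The 4.8% and 8.4% figures rest on the assumed 8.6% rate.

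**What to change.** For the DNAemia logistic models, replace the Wald sentence with: *Logistic models will be fitted by Firth penalised likelihood, with 95% profile penalised-likelihood intervals and penalised likelihood-ratio tests.* This corrects the fit as well as the interval, and it gives a finite estimate when a cell is empty.

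Also report the unadjusted difference in DNAemia rates with a score (Miettinen–Nurminen) interval, since the objectives are worded as rates.

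Do not derive standardised rates from the uncorrected Firth fit, because it pulls predicted probabilities toward 0.5. In the two-group case it adds 0.5 to each cell: 8.6% becomes (3.01 + 0.5)/36 = 9.75% and 86% becomes (30.1 + 0.5)/36 = 85.0%. The ratio is then about 0.115 instead of 0.10.

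Using fewer covariates would help but would not be enough alone: the excess is still about 19% with two covariates and 10% with none.

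Cost: a wording change, slightly less routine software and a somewhat smaller reported odds ratio. No new data or participants are needed.

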## **I. Hypotheses and Specific Aims**

### Hypotheses

- 1) Shingrix (RZV) recipients will have a lower rate of varicella-zoster virus (VZV) DNAemia after a live intradermal (ID) VZV challenge (vOka vaccine) than Zostavax (ZVL) recipients because of higher and/or more rapid VZV-specific T cell responses.
- 2) After a live VZV ID challenge, RZV recipients will have the same rate of VZV DNAemia whether the challenge was performed <1 or >5 years after vaccination; whereas ZVL recipients will have lower rates of VZV DNAemia if they are challenged <1 year after vaccinations compared with >5 years.
- 3) The peak memory VZV and/or gE Th1 responses to RZV mediate protective immune responses conferred by RZV against VZV DNAemia after VZV ID challenge; early responses may also play a role

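### The only mediation test specified is on a pooled immune score, so the T-cell (Th1) mechanism in Hypothesis 3 and in the causal clause of Hypothesis 1 has no test of its own

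*Combined protocol and SAP*

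**What the plan says.** Section I (Hypotheses) states a mechanism twice. Hypothesis 1 expects less DNAemia after RZV than after ZVL "because of higher and/or more rapid VZV-specific T cell responses". Hypothesis 3 is a mediation hypothesis with a named mediator: "The peak memory VZV and/or gE Th1 responses to RZV mediate protective immune responses conferred by RZV against VZV DNAemia after VZV ID challenge". It adds that early responses may contribute.

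Section IV.G, in the part on responses that limit viremia, gives the goal as finding "biomarkers that serve as intermediates in the pathway between virus challenge with DNAemia". The data are introduced as follows: "With all the matched measurements (transcriptomic, soluble marker, VZV-CMI T cell responses) on the same subjects". The test is then defined: "As a primary analysis, we will create a composite mediation score based on the following linear combination". The score is V = Σ β_m X_m, where β_m "denotes an association between molecule m with the exposure". V is standardised and tested, and it is the only mediator for which power is given: n = 70, outcome probability 56%, significance level 0.05, at least 80% power for an effect of 1.96.

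The number of molecules M, the list of components and the assay time points are not given, and no T-cell or Th1 sub-score is defined. Earlier in the same section, 35 per group is justified by "correlation analyses of our primary outcome measure with 2 measures of the immune responses". Those two measures are not named and may be clusters of analytes.

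**The concern.** A mediation hypothesis about one immune response needs a test in which that response is the mediator. Here the response is, at most, one contributor to a weighted sum. The weights reflect how strongly each molecule is associated with the exposure, not whether it is a T-cell measure. A large block of transcripts that differ by vaccine could dominate V.

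A positive result could then come from components other than Th1, and a null result could occur although Th1 is the mediator. Better weights would not cure this, because the quantity tested is not the one in the hypothesis. At stake is the trial's mechanistic conclusion. The comparison of DNAemia rates between vaccine groups is not affected.

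**Working it through.** **1. Which analysis in Section IV.G tests what**

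| Planned analysis | Question it answers | Mediation by a named T-cell measure? |
|---|---|---|
| Logistic regression of DNAemia on vaccine group | Rate difference (first clause of Hypothesis 1) | No |
| Correlation of DNAemia with two immune measures | Association; measures unnamed | No |
| Hotelling's T2 on flow-cytometric and soluble factors | Difference between groups | No |
| DESeq2 gene-expression comparisons | Difference between groups | No |
| GLM correlates (including Tconv), FDR-adjusted | Association | No |
| Composite V | Mediation | No; pooled, components undefined |

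Mediation requires that vaccine group shifts the marker and that the marker predicts DNAemia with vaccine group in the model. Only the last row addresses this, and only for V.

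**2. The plan's own figure**

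Inputs from Section IV.G: n = 70, p = 0.56, level 0.05 (taken as two-sided), power 80%, SD of V = 1. The correlation ρ between V and vaccine group is not stated. The usual logistic mediation formula is

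n = (z_{1−α/2} + z_{power})² / [b² · SD² · (1 − ρ²) · p(1 − p)].

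At ρ = 0: b = (1.960 + 0.842) / √(70 × 0.56 × 0.44) = 2.802 / 4.153 = 0.675, and e^0.675 = 1.96.

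So 1.96 reproduces as an odds ratio per SD with ρ = 0, although the text labels it a log odds ratio. Read literally as a log odds ratio, about 8 participants would suffice at ρ = 0. It would be the 80% limit at n = 70 only if ρ were about 0.94. The odds-ratio reading is used below.

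**3. Illustration: does V stand in for T cells?**

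All settings here are assumptions; none is in the documents.

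Simulation A: 35 per group; four T-cell markers driven by one latent T-cell response; 20, 200 or 2000 other molecules, 10% of which follow a separate vaccine-induced pathway. The vaccine shifts each latent response by 1 SD, and the true mediator has log OR 1.2 per unit. V is weighted by each molecule's correlation with vaccine group. V and a T-cell score are each tested in a logistic model with vaccine group. There were 1000 runs per setting (500 with 2000 molecules).

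| Other molecules | Mean correlation of V with T-cell score | T cells mediate: V / T-cell score significant | Other pathway mediates: V / T-cell score significant |
|---|---|---|---|
| 20 | 0.84 | 86% / 97% | 29% / 5% |
| 200 | 0.43–0.44 | 12% / 97% | 96% / 5% |
| 2000 | 0.31–0.32 | 6% / 97% | 97% / 3% |

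Simulation B: 86% versus 43% DNAemia, 0.8 SD vaccine shift, one Th1 marker as sole mediator with log OR 1.0 per SD. The Th1 test was significant in 86–89% of runs across two sets of runs. The composite was significant in 32–35% (10 markers), 13% (30) and 9% (100) with uncorrelated markers. At pairwise correlation 0.3 the range was 35–52%, and at 0.5 it was 48–64%.

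The direction is the same in both. The size depends on M and on the correlation between markers.

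**4. What named tests would cost**

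Minimum detectable odds ratio per SD at n = 70 and 80% power, by the formula above. The first Holm step for two tests uses α = 0.025, for which z = 2.241. At ρ = 0: b = (2.241 + 0.842) / 4.153 = 0.742, and e^0.742 = 2.10.

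| ρ (assumed) | α = 0.05 | α = 0.025 |
|---|---|---|
| 0 | 1.96 | 2.10 |
| 0.5 | 2.18 | 2.36 |
| 0.7 | 2.57 | 2.83 |
| 0.8 | 3.08 | 3.45 |
| 0.9 | 4.70 | 5.49 |

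At an odds ratio of 1.96 and ρ = 0, power goes from Φ(0.673 × 4.153 − 1.960) = 79.8% to Φ(2.795 − 2.241) ≈ 71%. Under Simulation B with log OR 0.675, a single Th1 test had about 56% power at 0.05 and 42% at 0.025.

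**The case against.** The strongest reply has four parts.

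- **V may be narrower than it looks.** A reader might infer that V sums every molecule measured. The text does not say so: the reference to all matched measurements describes the data at hand, and M is left open. This stands. The firm defect is that the components are unspecified, and with few other molecules V still tracks the T-cell score (correlation 0.84 with 20 others).
- **The hypotheses are tested in part.** A reader might infer that Hypotheses 1 and 3 can be neither confirmed nor refuted at all. That goes too far. The rate clause of Hypothesis 1 has its own logistic regression, Hypothesis 3 leaves room for early responses, and several analyses will give associational evidence on T cells. None of these is a mediation test of the named response.
- **A discovery score suits Secondary Objective 3**, which seeks the response characteristics that predict control. This stands as a reason to keep V. It does not supply the test that Hypothesis 3 calls for. The plan speaks of the mediation potential of markers in the plural, but details no marker-level test.
- **The simulated power gaps rest on chosen settings.** This also stands. They use larger effects than the plan's own 1.96 read as an odds ratio, and they test one marker at 0.05, not two under Holm.

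**Conclusion.** The concern holds as a gap in specification. Section IV.G contains no mediation test of a VZV- or gE-specific T-cell measure, so Hypothesis 3 and the causal clause of Hypothesis 1 would have to be judged from a pooled score with undefined content. A significant V cannot be credited to Th1, and a null V does not rule Th1 out.

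The size is unknown. In the simulations, with T cells as the true mediator, V was significant in anything from 6% to 86% of runs, depending on marker numbers and correlation. No particular loss of power should be quoted as the trial's own. The group comparison of DNAemia rates is not invalidated, and this point makes no stated sample size wrong.

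A named test would also have limits. In a further run of Simulation B with three other molecules controlling DNAemia and pairwise correlation 0.3, a non-mediating Th1 marker was significant in 44–47% of runs, and the composite in 86–96%. A significant named marker therefore supports causal mediation but does not prove it.

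**What to change.** In Section IV.G, in the part on responses that limit viremia:

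1. Pre-specify a mediation test of one VZV-specific and one gE-specific Th1 measure at the peak-memory time point of Hypothesis 3, with vaccine group as the exposure and Holm at 0.05. Name it as the test of Hypothesis 3 and of the causal clause of Hypothesis 1.
2. State which scheduled draw counts as peak memory. In Cohorts 1 and 2 the draws begin on the challenge day. If peak memory means soon after vaccination, this protocol schedules such samples only in Part B, and the plan should say how Part A is handled. If the sponsor also wants to claim more rapid responses under Hypothesis 1, an early time point must be named too.
3. Keep V as the discovery analysis for Secondary Objective 3, list its components and time points, and base no Th1 claim on V alone.

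The two measures should not be presented as those in the sample-size paragraph, which are unnamed and may be clusters.

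The cost is SAP wording. VZV- and gE-specific T-cell responses are already secondary endpoints in Section IV.A, so no new type of assay is needed. The price of two tests is a minimum detectable odds ratio per SD of about 2.10 instead of 1.96 at ρ = 0, with both figures rising as ρ rises.

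### The composite mediation score adds markers in different units, scales only the total and leaves the weight undefined, so under the usual readings of the weight it depends on assay units

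*Combined protocol and SAP*

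**What the plan says.** In Section IV.G (Data Analysis Plan), the part on systemic and local immune responses that limit viremia describes the mediation analysis. It draws on several assay types: "With all the matched measurements (transcriptomic, soluble marker, VZV-CMI T cell responses) on the same subjects". As its primary mediation analysis, "we will create a composite mediation score based on the following linear combination", namely V_i = Σ β_m X_mi. The weight β_m "denotes an association between molecule m with the exposure", and X_mi "is the measurement on molecule m for subject i". The only scaling step comes after the sum: "Upon standardizing V, we then can test for mediation using the approach in" the cited sample-size paper for mediation.

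Two nearby sentences could be taken to cover preprocessing, but each belongs to another analysis. The log transform is conditional and tied to Hotelling's test: "If necessary, outcome measures will be log-transformed in order to better satisfy the assumptions of the T2 method". Dimension reduction appears in the justification of 35 per group for the correlation analyses, where immune measures are described as ones "which may represent clusters of several analytes that group together using PCA or other dimensionality reduction method". Neither is linked to V.

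**The concern.** Scaling a sum after it is formed cannot change the relative weight of its parts. If the parts are in different units, the mix may be set by how each laboratory reports its results. Two analysts following the same text could build different scores from the same data, one with a cytokine in ng/ml and the other in pg/ml, or one with slopes as weights and the other with correlations. The score is the main mediation test serving Secondary Objective 3 and Hypothesis 3, so a finding of mediation, or of none, could be an artefact of units. The primary DNAemia comparisons are not affected.

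**Working it through.** **Inputs.** From Section IV.G: n = 70 ("Sample size: Sample size is 70"), outcome probability 0.56, α = 0.05 (taken as two-sided), power 80%, V standardised. The paragraph does not name the exposure. I take it to be vaccine group, since every participant is challenged. The plan gives no marker SDs or effect sizes, so all of those below are assumptions.

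**1. The plan's own figure.** The smallest detectable effect per SD of V is b = (z₀.₉₇₅ + z₀.₈₀) / √[n p (1−p) (1−ρ²)], where ρ is the correlation of V with exposure. With ρ = 0:

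b = (1.960 + 0.842) / √(70 × 0.56 × 0.44) = 2.802 / √17.248 = 2.802 / 4.153 = 0.675, and exp(0.675) = 1.96.

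The stated 1.96 is thus recovered as an odds ratio, although the text labels it a log odds ratio; that labelling is a separate matter. For the present point, the formula takes V with SD 1, and nothing about the scaling of the components enters it.

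**2. Effect of a change of units.** Multiply the unit of X_m by c and follow β_m X_m:

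- β_m is the slope of marker on exposure: β_m is multiplied by c, so the term is multiplied by c². From ng/ml to pg/ml (c = 1,000) the factor is 1,000,000.
- β_m is a correlation: β_m is unchanged, so the factor is c, here 1,000.
- β_m is a per-unit coefficient from regressing exposure on marker: β_m is divided by c, so the term is unchanged.

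A constant added to X_m shifts every V_i equally and drops out when V is standardised. Spread therefore matters, not numerical level.

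**3. Two markers by hand.** Assume a true mediator with within-group SD 1 and a vaccine difference of 0.8 SD, and an irrelevant marker with SD k and a difference of 0.3 SD. The within-group SD of each term in V is:

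- Slope weights: 0.8 × 1 = 0.8 against 0.3k × k = 0.3k². For k = 1, 3, 10, 100 the second term is 0.3, 2.7, 30, 3,000.
- Correlation weights, r = d/√(d² + 4): 0.8/√4.64 = 0.371 against (0.3/√4.09) × k = 0.148k, that is 0.148, 0.445, 1.48, 14.8.

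With slope weights, or with correlation weights, the irrelevant marker already outweighs the mediator at k = 3.

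**4. Simulated power of the test of V.** Same two markers, 35 per group, log OR −0.9 per within-group SD of the true mediator; logistic model of outcome on V and vaccine, Wald p < 0.05. The intercept is a further assumption. Ranges are across repeat runs:

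| Weight | k = 1 | k = 3 | k = 10 | k = 100 |
|---|---|---|---|---|
| Slope of marker on exposure | 79–81% | 23–26% | 6–7% | 5–6% |
| Correlation | 78–83% | 52–56% | 21–25% | 5–7% |
| Per-unit coefficient of exposure on marker | 77–83% at all k | | | |
| Slope, each marker scaled first | | | | 80–83% |

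With slope weights at k = 100, V correlates 1.00 with the irrelevant marker and 0.09 with the true mediator; on a common scale the latter is 0.95.

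A second setting (mediator difference 1 SD, log OR −1.2; 400 runs) gave the same pattern at k = 1, 3, 10, 100: slope 95%, 36%, 9%, 2%; correlation 95%, 71%, 31%, 4%; per-unit coefficient 95–96% throughout; markers scaled first 94–95% throughout.

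**5. The reverse case.** With slope weights and the true mediator's scale 10 or 100 times larger, power is 91–92%, against 79% at equal scale.

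**The case against.** The strongest reply is that this is an omission, not a demonstrated failure. The text never says that the measurements are unprocessed. An analyst may well normalise transcripts and log-transform cytokines before summing. After a log transform, a change of unit only adds a constant, which drops out of V, so differences in spread would remain but unit dependence would not. The weight is also left open, and one admissible reading is free of units. All of this stands, and it rules out a tempting stronger reading, that the marker with the largest numbers must determine the score and a true mediator must be lost. That would need a definition of β_m that the plan does not give, and step 5 shows that a scale difference can equally favour the mediator.

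A reader might also infer that the stated 80% power is wrong. It is not, on this ground: it is conditional on an effect of a given size for a standardised V, however V is built. A badly built V may have a smaller true effect, which is a different statement.

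Finally, scaling each marker is not a complete remedy. With slope weights, all markers at within-group SD 1 and extra irrelevant markers that each differ by 0.3 SD between vaccines, power fell to 59% with 5 such markers, 26% with 20 and 7% with 100 (400 runs). With transcripts among the inputs, the number of markers may be large.

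The reply does not remove the gap: nothing in Section IV.G selects the unit-free weight or states any marker-level scaling for this score.

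**Conclusion.** The point holds as one of specification. Followed literally, with a slope or a correlation as the weight, the primary mediation score depends on assay units and can be dominated by the marker with the largest spread. With a per-unit coefficient of exposure on marker it does not, and the plan does not say which is meant. In the assumed two-marker setting, power drops from about 80% to about 25% (slope) or 55% (correlation) at a 3-fold difference in spread, and to near the 5% test level at 100-fold. These figures rest on assumed effect sizes, scale ratios and marker number, so they show mechanism and direction, not expected power in this trial. The analysis is secondary. The matter should be settled before the score is computed.

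**What to change.** State in Section IV.G:

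1. what β_m is: the estimator, the direction of the regression and the exposure;
2. that skewed markers are log-transformed where needed;
3. that each X_m is then centred and scaled to SD 1 (for example the pooled within-group SD), giving Z_mi, before β_m is estimated;
4. that V_i = Σ β_m Z_mi, with V then standardised as already planned.

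The cost is a sentence or two, with no new data and no change to the stated sample size or power figure. There is a small downside: equal scaling gives more total weight to the assay type with the most markers, and it does not stop many irrelevant markers from diluting V. It removes the dependence on units but does not guarantee the simulated power.
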